- Group 2: Joint Line Landmark Based (sham Ultrasound)
- Group 3: Suprapatellar Ultrasound Guided
- Group 4: Suprapatellar Landmark Based (sham Ultrasound)

The patients will be blinded to their group assignment prior to the first injection and will not be able to see which technique is employed. The provider performing the injections will not be blinded. The third injection (only) will be different in that contrast medium will be injected along with the hyaluronan. Following the third injection, fluoroscopy will be used to determine presence/absence of the contrast medium into the joint. The radiologist interpreting these images will be blinded to the technique employed. At 3 months following the third injection, the patients will be contacted by a surveyor blinded to the group assignment.

Objectives and Specific Aims

- 1. To compare the accuracy of injections into the knee joint with two different approaches, joint line and suprapatellar pouch
- 2. To determine if the addition of ultrasound guidance to traditional landmark-based techniques enhances the accuracy of these techniques
- 3. To examine differences in patient perceived pain and functioning of their knee joint following the injection series.

Medical Application

Injections into the knee joint are an exceedingly common procedure by a variety of specialists, primary care physicians, and non-physician clinicians. Knowledge of the most accurate and clinically effective injection technique will positively impact countless future patients. If we find that the addition of ultrasound guidance increases accuracy, as

we hypothesize, patient-oriented results should be better with fewer complications. This will allow the patient to return to activity quicker.

Background and Significance

Literature Review (as of 18 November 2010) and Preliminary Data and/or Findings.

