• Initial evaluation: Screening instrument for first visit (history and physical, diagnostic and inclusion/exclusion criteria), WOMAC (prior to receiving each of the three injections), and intervention

The clinical staff will collect the following data:

- Name, email, phone number
- Demographics: age, gender, type and number of injections received previously
- Informed consent/HIPAA document
- WOMAC Osteoarthritis Index
- Post Procedure

The Injecting physician will record the following data:

- Group Assignment
- Amount and type of therapeutic substance injected
- Total time to complete procedure from sterilization to bandaging
- Procedural Pain Score (0 to 10)
- Procedural Satisfaction Score (0 to 10)
- Complications

In a separate electronic database, the radiologist will record the following data:

- Name
- Presence or absence of contrast material within the knee joint
- Three months after intervention (telephone)
 - WOMAC Osteoarthritis Index
 - Procedure Satisfaction Score (0 to 10)

Study Time Line

Assessment					
Study Day /	Initial Evaluation	and	Second	Third Injection	3 months
Period	First Injection		Injection	With contrast	Post Treatment
Screening	Х				
Informed	Х				
Consent, discuss					
Plan, etc.					
Randomization	Х				
Demographics,	Х				
History &					
Physical					
WOMAC (pre	х		Х	Х	Х
injection)					
Treatment	X		Х	Х	
Procedural Pain	Х		Х	Х	
(post injection)					
Procedural	Х		Х	X	Х

Satisfaction (post injection)			
Fluoroscopic Analysis		Х	
Complications (post injection)		X	

Statistical Consideration

Primary endpoints are presence/absence of contrast medium in the joint, the WOMAC osteoarthritis index, and overall satisfaction with the injection technique. Our statistical analysis of the WOMAC index will consider a mean change from baseline to post-injection with the variables of pain, stiffness, and function. We will also study the mean change of the Global Score from the WOMAC.

Data Analysis

Statistical analysis of the WOMAC score will consist of one-way analysis of variance (ANOVA) followed by Tukey's post-hoc multiple comparisons between the four groups with a 5%, two-sided familywise significance level (which allows for comparisons between all possible pairs of treatments). Chi square tests will be used to compare the percent accuracy among the four groups. We will also perform sub-analysis to determine if any trends can be linked to the type of medication (viscosupplementation) injected versus accuracy.

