Safety Monitoring and Analysis Plan

Since treatments are provided at the onset of the study, "stopping rules" will not apply in this study. Since the primary outcome includes pain and functioning at baseline and 3 months following the intervention, the entire study must be carried out in order to gather the desired data. There have been no unexpected side effects other than local pain and swelling at the injection site that have been reported in the studies using these injection techniques, so we do not believe any other specific side effects will need to be monitored. Patients will not be included in the study if a contraindication applies to them. Of note, viscosupplementation is not contraindicated in pregnant patients.

Sample Size Estimation

For the comparison of accuracy, a two group chi square test with a 5% two-sided significance level will have 80% power to detect a difference of 33 percentage points between groups when the accuracy in the less-accurate condition is 60% and the sample size in each group is 25.

Previous studies have demonstrated an effect size of the WOMAC ranging from 0.5 to 1.0 when medication interventions were studies on patients with knee pain. A sample size of 25 in each group will have 80% power to detect an effect size of 0.809 using a two group t-test with a 5% two-sided significance level.

Reference: Lenth, R. V. (2006-9). Java Applets for Power and Sample Size [Computer software]. Retrieved November, 2010, from http://www.stat.uiowa.edu/~rlenth/Power.

Reporting Adverse Events

Definitions:

Adverse events (adverse effects, adverse reactions): any occurrence of injury, dysfunction, disease, or abnormality of any organ or tissue that occurs in a subject enrolled in a clinical protocol. Manifestations of an adverse event may include symptoms, physical exam abnormalities, diagnostic study abnormalities, and/or death.

Expected adverse events: adverse events previously known or anticipated to result from: 1) the interventions and interactions used in the research (these events must be included as potential risks in the consent form); 2) the collection of identifiable private information under research (these events must be included as potential risks in the consent form); 3) an underlying disease, disorder, or condition of the human subjects; and/or 4) other circumstances unrelated to the research or any underlying disease, disorder, or condition of the subject.

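### The stated 80% WOMAC power is for one unadjusted t-test, not the planned Tukey comparison (60% for a named pair at 25 per group); the accuracy tests are not tied to Aims 1 and 2

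*Combined protocol and SAP*

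**What the plan says.** **WOMAC.** Data Analysis plans a one-way ANOVA followed by Tukey's "post-hoc multiple comparisons between the four groups with a 5%, two-sided familywise significance level", described as a level "which allows for comparisons between all possible pairs of treatments". Sample Size Estimation says "A sample size of 25 in each group will have 80% power to detect an effect size of 0.809 using a two group t-test" at a two-sided 5% level. It cites effect sizes of 0.5 to 1.0 from earlier studies of medication.

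**Accuracy.** Objectives and Specific Aims sets two factor questions. Aim 1 is "To compare the accuracy of injections into the knee joint with two different approaches, joint line and suprapatellar pouch". Aim 2 is "To determine if the addition of ultrasound guidance to traditional landmark-based techniques enhances the accuracy of these techniques". The four groups cross these factors: 1 joint line guided, 2 joint line landmark, 3 suprapatellar guided, 4 suprapatellar landmark. The accuracy analysis is one sentence: "Chi square tests will be used to compare the percent accuracy among the four groups". The sizing says "a two group chi square test with a 5% two-sided significance level will have 80% power" for a "difference of 33 percentage points between groups when the accuracy in the less-accurate condition is 60" per cent, with 25 per group. It does not say which two groups are meant.

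**Group size.** Both power statements use 25 per group. Study Design allows for 120 patients, at most 30 in each group. No dropout rate is given.

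**The concern.** The WOMAC power statement and the WOMAC analysis describe different tests. Tukey's procedure holds the error rate across six pairs at 5%, so each pair faces a stricter threshold than a lone t-test. A reader would take 80% as the chance of detecting a 0.809 difference between, say, groups 1 and 2, and under the planned analysis it is lower.

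For accuracy, the aims fix the two factors in advance but the test is left open. The sentence could mean one test with 3 degrees of freedom, a set of pairwise tests (suggested by the plural and by the two-group sizing), or pooled factor comparisons. These can lead to different conclusions, and nothing stops the choice being made after the data are seen. The same six pairs get familywise control for WOMAC and none is written for accuracy, although both are listed as primary endpoints.

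**Working it through.** **Inputs.** Effect size 0.809, 25 per group, two-sided 5% (Sample Size Estimation); four groups, Tukey, familywise 5% (Data Analysis); cap of 30 per group (Study Design); accuracy 60% v 60 + 33 = 93% (Sample Size Estimation).

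**1. The stated WOMAC figure.** Noncentrality = d × √(n/2) = 0.809 × √12.5 = 2.860. With 48 degrees of freedom the critical |t| is 2.011, and the noncentral t gives 80.0%. The figure reproduces. With 30 per group (58 degrees of freedom) it is 86.9%.

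**2. The planned Tukey comparison, one named pair.** Critical |t| = q(0.95; 4, 4n − 4)/√2, with the variance pooled over four groups.

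| | 25 per group | 30 per group |
|---|---|---|
| Degrees of freedom | 96 | 116 |
| Critical \|t\| | 3.698/√2 = 2.615 | 3.686/√2 = 2.607 |
| Noncentrality at 0.809 | 2.860 | 3.133 |
| Power at 0.809, Tukey | 59.8% | 70.0% |
| Power at 0.809, unadjusted | 80.0% | 86.9% |
| Tukey power at 0.5 | 20% | 26% |
| Tukey power at 1.0 | 82% | 90% |
| Effect for 80% Tukey power | 0.98 | 0.89 |

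The level per pair is about 1.04%. Requiring a significant ANOVA first changes little: 58-60% and 68-70% by simulation, depending on the other two means.

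**3. At least one significant Tukey pair.** This depends on all four means. By simulation with 25 per group and a largest difference of 0.809, it is about 65% if the other two means lie midway, 83% if one group differs from three equal ones, and 89% if two groups differ from two.

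**4. The stated accuracy figure.** Using the pooled-variance normal approximation, z = (0.33 − 1.960 × √(2 × 0.765 × 0.235/25)) / √((0.60 × 0.40 + 0.93 × 0.07)/25) = (0.33 − 0.2350)/0.1105 = 0.86, so power is 80.5%. It reproduces as a single unadjusted test.

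**5. Accuracy error rate if six pairs are tested unadjusted.** The chance of at least one significant pair when all four groups share one rate, by exact enumeration of the Pearson chi-square without continuity correction:

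| Common rate | 25 per group | 30 per group |
|---|---|---|
| 60% | 23.5% | 19.6% |
| 77.3% | 21.5% | 19.3% |
| 90% | 20% | 22% |
| 93% | 15% | 19% |
| 95.6% | 6% | 10% |

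**6. The choice of contrast matters.** Power at 60% v 93%, each test at 5%, for 25 / 30 per group. Which groups benefit is an assumption.

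| Pattern | Guidance test stratified by approach | Four-group test |
|---|---|---|
| Guidance helps both approaches | 99% / 99.6% | 95% / 98% |
| Only guided suprapatellar benefits | 43% / 51% | 82.5% / 91% |

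**The case against.** The strongest reply on WOMAC is that Sample Size Estimation names its test openly, the arithmetic is right, and 0.809 is offered as what 25 per group can detect, not as the expected effect. All of that stands. What remains is a mismatch: under the analysis the plan specifies, 0.809 is not detectable with 80% power for a named pair.

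A reader might infer that the planned WOMAC analysis as a whole has only 60-70% power. The documents do not support that. The figure belongs to one named pair, its two ends are different group sizes, and the chance of some significant pair can be well above 80% (step 3). A reader might also infer that 120 patients are too few. That does not follow either. A named pair would need 37 per group for 80% at 0.809, but nothing in the plan says that 0.809 is the difference the trial must detect.

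On accuracy, the plan nowhere says that pairs will be tested unadjusted. Under a single four-group test the inflation in step 5 does not arise, and it shrinks at high accuracy rates. So an inflated error rate is a possibility left open, not a planned one.

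One could also object to pooled factor tests as the remedy. Aim 2 can be read as asking about guidance within each approach. The background also hypothesises that guided suprapatellar injection will be the most accurate when fluid is present, and in that pattern pooling loses much power (step 6). This stands, and the choice should be the sponsor's.

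**Conclusion.** The WOMAC statement needs correcting. The 80% applies to an unadjusted two-group t-test. The like-for-like figure for a named pair under Tukey is 60% with 25 per group, a loss of 20 points. With all 30 per group analysed it is 70% against 87%, a loss of 17 points. These figures assume equal group sizes, a common variance and roughly normal data.

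The accuracy gap is real but secondary. It is one of interpretation and error control, not evidence that the sample is too small. Its size depends on what the sentence means: about 15-24% familywise error for common rates of 60-93% if six unadjusted pairs are intended, and no inflation but no answer to either aim if one four-group test is intended. Naming the comparisons settles it under either reading. Multiplicity across the three primary endpoints is a separate matter that this point does not resolve.

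**What to change.** **Sample Size Estimation, WOMAC.** Replace the 80% statement with, for example: *For any one named pair under Tukey's procedure at a 5% familywise level, power at an effect size of 0.809 is 60% with 25 per group and 70% with 30; 80% power requires an effect of 0.98 or 0.89 respectively. The chance of at least one significant pair depends on all four means.* State whether 25 or 30 per group are expected to be analysed. The ANOVA with Tukey can stay.

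**Data Analysis, accuracy.** Name in advance the comparisons that answer each aim. For example, use groups 1 v 2 and 3 v 4 for guidance (Aim 2) and 1 v 3 and 2 v 4 for approach (Aim 1), or the stratified equivalents, Holm-adjusted at a two-sided 5%. This matches the control already given to WOMAC. Pooled tests gain power if an effect is common to both levels of the other factor and lose it if only guided suprapatellar benefits, so the sponsor should choose between them now.

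**Cost.** Wording only: no added patients, visits or data. The stated WOMAC power becomes less favourable. The accuracy power should also be labelled as unadjusted or restated. With four Holm-adjusted comparisons the strictest step is 5%/4 = 1.25%, where the formula in step 4 (2.498 in place of 1.960) gives (0.33 − 0.2995)/0.1105 = 0.28, or 61% power, with 25 per group, and (0.33 − 0.2734)/0.1008 = 0.56, or 71%, with 30.

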Unexpected adverse events /Unanticipated problems: adverse events that 1) are not expected given the nature of the research procedures and the subject population being studied; and 2) suggest that the research places subjects or others at a greater risk of harm or discomfort related to the research than was previously known or recognized.

Serious adverse event: an adverse event that is fatal, life-threatening, permanently disabling, require inpatient hospitalization, or result in congenital anomalies/birth defect, overdose or cancer, or any other adverse event that, based on appropriate medical judgment, may jeopardize the subject's health and may require medical or surgical intervention to prevent one of the other outcomes listed above.

Expected Adverse Events from Research Risks and Reporting

- Rare but serious (Event Rate < 1%): infection at the site of injection; contrast dye allergic reaction.
- Likely (5% ≤ Event Rate < 10%): 8% incidence of pseudo-synovitis with the use of Synvisc® products.
- More likely (Event Rate ≥ 10%): bruising, swelling and increased pain at site of injection for several days to a few weeks.

Monitoring of adverse clinical events will be done during each of the two scheduled followup assessments. These will be managed as follows:

- Infection at injection site, or blood-borne infection: manage as clinically indicated based on assessment by physician.
- Contrast dye reaction: treat as clinically indicated based on severity.
- Pseudo-synovitis: NSAIDs, ice, compression, elevation.
- Bruising, swelling and increased pain at site of injection: treat with compression, ice, and prescribed pain medications (no NSAIDs), and patient reassurance that these resolve with time.

Reporting Serious and Unexpected Adverse Events to the IRB

Serious Adverse Events: The PI, within one working day, will report all serious adverse events (SAE) occurring in subjects enrolled in the study. This is accomplished by submitting an adverse event report memorandum to the IRB. Serious adverse events will be reported even if the PI believes that the adverse events are unrelated to the protocol.

Unexpected (but not serious) adverse events occurring in subjects enrolled in the study, in the opinion of the PI, are possibly related to participation in the protocol will be reported by the PI within 10 (ten) working days to the IRB using the same procedure.

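### The safety plan sees no need to monitor specific effects beyond local pain and swelling, yet the protocol lists other expected events, promises to monitor them, and gives the three-month call no item to record them

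*Combined protocol and SAP*

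**What the plan says.** The Safety Monitoring and Analysis Plan reasons from past studies of the injection techniques: "There have been no unexpected side effects other than local pain and swelling at the injection site that have been reported". It then concludes: "so we do not believe any other specific side effects will need to be monitored".

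The section Expected Adverse Events from Research Risks and Reporting lists:

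- "Rare but serious (Event Rate < 1%): infection at the site of injection; contrast dye allergic reaction";
- under a 5% to 10% tier, "8% incidence of pseudo-synovitis with the use of Synvisc® products";
- at 10% or more, "bruising, swelling and increased pain at site of injection for several days to a few weeks".

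The same section says that adverse clinical events will be monitored at two follow-up assessments, and it gives a management line for each listed type.

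On collection, the Data Collection section has the injecting physician record Complications, with no event types named. Study Design states that this physician is not blinded. The Study Time Line has one Complications row, labelled post injection, with a single mark. For the three-month call, Data Collection lists the WOMAC and satisfaction, and Appointment 4 adds other therapies used since the injection. Neither mentions adverse events.

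**The concern.** Staff cannot follow both sections. One says that nothing specific beyond local pain and swelling needs watching. The other names further events, two of them labelled serious, and promises to monitor them.

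The stated reason does not carry the conclusion. It rests on studies of techniques, whereas a contrast reaction comes from the contrast agent and the protocol ties pseudo-synovitis to particular products. Human Use Justification gives contrast reaction as the only additional risk of taking part. Read literally, the clause leaves the one risk attributed to the research itself outside specific monitoring.

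At stake is the completeness of the safety data. Events that the protocol expects may go unrecorded once the third visit ends, or be recorded differently from one physician to another. A descriptive table by group would then be hard to rely on.

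**Working it through.** **Where each section leaves an expected event**

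| Question | Safety Monitoring and Analysis Plan | Expected Adverse Events section | Data Collection, Time Line, Appointment 4 |
|---|---|---|---|
| Infection, contrast reaction, pseudo-synovitis | no specific monitoring | expected; monitoring promised | not named; one Complications item |
| Local pain and swelling | described as unexpected | expected, 10% or more | not named; one Complications item |
| When | not stated | two follow-up assessments | three injection visits and one call; one mark in the Complications row (its column is uncertain in the extracted text) |
| Who records | not stated | not stated | unblinded injecting physician; no adverse-event item for the Surveyor |

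The third injection is the only one with contrast. After that visit the only planned contact is the call, and its lists contain no adverse-event item. The protocol itself expects local reactions to last from days to weeks, so some expected events run past the visit. The reporting rules do not close the gap. Serious events, and unexpected ones thought possibly related, go to the IRB, but pseudo-synovitis is listed as expected and is not labelled serious. Unless a case is serious, its only specified record is the Complications item.

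**The plan's own figures.** No sample size or power is stated for complications. The two calculations given do reproduce. For accuracy of 60% against 93% with 25 per group, power is 0.805. For a WOMAC effect size of 0.809 with 25 per group, it is 0.800. Neither bears on safety.

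**How many events might occur.** Inputs: N = 120 (Study Design), 8% with Synvisc products, and a ceiling of 1% for each rare serious type (both from the expected-events list).

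- Pseudo-synovitis: expected cases = N × 0.08 × s, where s is the share receiving a Synvisc product. The documents do not give s. At s = 0 this is 0. At s = 1 it is 120 × 0.08 = 9.6, or 30 × 0.08 = 2.4 per group.
- One rare serious type: P(at least one) = 1 − (1 − p)^N.
  - p = 1% (ceiling): 1 − 0.99^120 = 0.70
  - p = 0.5% (assumed): 1 − 0.995^120 = 0.45
  - p = 0.1% (assumed): 1 − 0.999^120 = 0.11

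The rates are read as per participant, because the protocol does not state the unit. Read per injection, the infection figure would be higher, since each participant has three injections.

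**Would complete recording allow a comparison?** For illustration, suppose every participant receives a Synvisc product and ultrasound halves the rate, 8% to 4% (the halving is an assumption). Compare the pooled ultrasound and landmark arms, 60 against 60:

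- z = [0.04 − 1.96 × √(2 × 0.06 × 0.94/60)] / √((0.08 × 0.92 + 0.04 × 0.96)/60) = (0.04 − 0.0850)/0.0432 = −1.04
- power is about 15% by this normal approximation and about 6% by Fisher's exact test
- 80% power would need 553 per arm

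**The case against.** The best case for the plan has four parts.

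1. The expected-events section is the more specific text. It commits to monitoring and names the events, so a careful site would follow it. Complications is a recorded item, and every serious event must reach the IRB within one working day, whatever its presumed cause. This stands in part: events are not wholly unsought. But the documents do not say which section prevails, and the commitment has no matching item at the call.
2. The safety plan speaks of unexpected effects of techniques, while the list gives expected events, some from product or contrast. This is correct. Listing those events is not itself contradictory; only the conclusion about monitoring conflicts. The clause also says specific side effects, which is weaker than a bar on recording others.
3. The case report form is not in the documents, so the real form may be more detailed than the list. This too is fair. The point therefore rests on the plan as written, and chiefly on the absence of any adverse-event item at the call.
4. Tick-boxes completed by unblinded physicians remain unblinded. This stands for the injection visits. It does not apply to the call, where the Surveyor is blinded.

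A reader might also infer that the trial cannot test a hypothesis of fewer complications. The documents do not support that as a criticism. Medical Application says that "patient-oriented results should be better with fewer complications", but as something that should follow if accuracy improves. Complications appear in none of the three aims, the primary endpoints, the data analysis or the sample size. Low event counts would leave such a comparison underpowered even with perfect recording.

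**Conclusion.** The conflict is real but narrow. One clause about monitoring contradicts the expected-events section, and the data-collection plan does not carry out the monitoring which that section promises. The practical gap is greatest after the third injection, where no planned item collects adverse events.

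The size can be given only as a range: 0 to about 10 pseudo-synovitis cases, and at most about a 70% chance of seeing a given rare serious event at all. This assumes that all 120 participants are treated and that rates are per participant. It would be wrong to read these figures as the number of events missed, because the documents give no basis for estimating that. The primary endpoints are not affected. The case for a change rests on safety data and on consistency of the protocol.

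**What to change.** - In the Safety Monitoring and Analysis Plan, remove the closing clause about other side effects and refer to the expected-events list. In the same edit, reconcile the description of local pain and swelling as unexpected with their listing as expected, and the two follow-up assessments with the actual schedule of three visits and one call.
- In Data Collection and the Time Line, replace the single Complications item with a yes/no and a date for each of the four listed types (infection, contrast reaction, pseudo-synovitis, local reaction). Use the same wording in all four groups at each contact already planned.
- At the three-month call, have the blinded Surveyor ask these questions after the WOMAC and satisfaction items, so that they cannot colour those answers.
- In Data Analysis, add a descriptive table of each event type by group, with no significance test.

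The cost is a short text edit and a few more questions at existing contacts, including the call. No visit is added and no change to clinical management is proposed. Two limits remain: entries at the injection visits still come from unblinded physicians, and answers at the call depend on recall over three months.
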